10.1 Sample Size Estimation

Subjects with C1-INH HAE

Seven subjects assigned to each treatment (Placebo, or [REDACTED] mg, [REDACTED] mg, or [REDACTED] mg CSL312 q4wk) are needed to reach power of ~82% for the comparisons of [REDACTED] mg CSL312 q4wk versus placebo q4wk and [REDACTED] mg CSL312 q4wk versus placebo q4wk in Treatment Period 1. This is based on the following assumptions:

- The time-normalized number of HAE attacks is 2.9 attacks per month during treatment with placebo. This number was derived from CSL study CSL830_3001, using the lower bound of the distribution-free 95% confidence interval for the median of the first placebo treatment period.
- The time-normalized number of HAE attacks is 0.6 attacks per month during treatment with [REDACTED] mg CSL312 q4wk or [REDACTED] mg CSL312 q4wk. The number was derived from CSL study CSL830_3001, using the upper bound of the distribution-free 95% confidence interval for the median of the combined active treatment periods.
- Alpha is 2.5% for each of the 2 two-sided Mann-Whitney Tests of [REDACTED] mg CSL312 q4wk or [REDACTED] mg CSL312 q4wk against placebo.

[REDACTED]

[REDACTED]. The sample size of 7 subjects for this arm is not driven by an efficacy comparison, but instead, by consistency with other treatment arms and for maintenance of blinding of the study. No testing for efficacy of the [REDACTED] mg CSL312 dose against placebo is planned and no power calculation has been done. An additional subject may be added to each of these 4 treatment arms to account for drop outs during Treatment Period 1, resulting in 8 subjects in each treatment arm.

Up to 7 subjects with C1-INH HAE will be assigned to receive [REDACTED] mg CSL312 q2wk. This arm is included for informational purposes, and therefore no testing against placebo is planned and no power calculation has been done. An additional subject may be added to this arm to account for drop outs during Treatment Period 1, resulting in up to 8 subjects in this treatment arm.

Overall, a total of up to 40 subjects with C1-INH HAE will be assigned to treatment in Treatment Period 1.

Subjects with FXII/PLG HAE

Up to 10 subjects with FXII/PLG HAE will take part in the study.

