### 4.2.1 Primary Study Hypothesis

To test for a difference in the primary efficacy endpoint between [CCI] mg CSL312 q4wk or [CCI] mg CSL312 q4wk and placebo q4wk, pairwise comparisons will be performed by testing the hypotheses using a two-sided Mann-Whitney test.

To account for multiple testing, the alpha level of 5% will be evenly split between the two hypotheses tested. Details are given in Section 10.1.

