## 4.5 Determination of the Sample Size

### Subjects with C1-INH HAE

Seven subjects assigned to each treatment (placebo, or [REDACTED] mg, or [REDACTED] mg CSL312 q4wk) are needed to reach a power of ~82% for the comparisons of [REDACTED] mg CSL312 q4wk against placebo q4wk and [REDACTED] mg CSL312 q4wk against placebo q4wk in Treatment Period 1.

This is based on the following assumptions:

- Alpha is 2.5% for each of the 2 two-sided Mann-Whitney tests of [REDACTED] mg CSL312 q4wk or [REDACTED] mg CSL312 q4wk against placebo q4wk.
- The time-normalized number of HAE attacks is 2.9 attacks per month during treatment with placebo. This number was derived from CSL study CSL830\_3001, using the lower bound of the distribution-free 95% confidence interval (CI) for the median of the first placebo treatment period.
- The time-normalized number of HAE attacks is 0.6 attacks per month during treatment with [REDACTED] mg or [REDACTED] mg CSL312 q4wk. The number was derived from CSL study CSL830\_3001, using the upper bound of the distribution-free 95% CI for the median of the combined active treatment periods.
- For the time-normalized number of HAE attacks during CSL321 treatment and placebo a Poisson distribution is assumed. The lower bound and the upper bound, respectively, of the CIs for the medians are chosen for the rate parameters.
- Randomization allocation between CSL321 treatment and placebo which are compared are equal.

[REDACTED]

[REDACTED]. The sample size of 7 subjects for this arm is not driven by an

efficacy comparison, but instead, by consistency with other treatment arms and for maintenance of the blinding of the study. No testing for efficacy of the [REDACTED] mg CSL312 dose against placebo is planned and no power calculation has been done.

An additional subject will be added to each of these 4 treatment arms to account for dropouts during Treatment Period 1, resulting in 8 subjects required in each treatment arm.

Up to 7 subjects with C1-INH HAE will be assigned to receive [REDACTED] mg CSL312 q2wk. This arm is included for informational purposes, and therefore no testing against placebo is planned and no power calculation has been done. An additional subject will be added to this arm to account for dropouts during Treatment Period 1, resulting in up to 8 subjects in this treatment arm.

Overall, a total of up to 40 subjects with C1-INH HAE will be assigned to treatment in Treatment Period 1.

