## **4.6 Planned Interim Analyses and Reviews**

### **4.6.1 Interim Analyses**

A first interim analysis will be conducted after all C1-INH HAE subjects who received placebo or [REDACTED] mg, [REDACTED] mg, or [REDACTED] mg CSL312 q4wk have completed Treatment Period 1 using data from all subjects available at this time. The confirmatory test of [REDACTED] mg or [REDACTED] mg CSL312 q4wk against placebo q4wk will not be performed for any dry run. It will only be performed for the interim analysis.

[figure not shown]
A second interim analysis will be conducted after all subjects with C1-INH HAE who received [REDACTED] mg CSL312 q2wk and subjects with FXII/PLG HAE have completed Treatment Period 1 using data from all subjects available at this time. This interim analysis will include subjects with C1-INH HAE and with FXII/PLG HAE with all available data collected up to this time point.

No separate interim analysis will be conducted after subjects with FXII/PLG HAE have completed Treatment Period 1.

The interim analyses should provide information about the efficacy, safety and PK/**CCI** of **CCI** mg, **CCI** mg, and **CCI** mg CSL312 q4wk (**CCI** **CCI**) and **CCI** mg CSL312 q2wk.

Each interim analysis will be presented as outlined in Section 7 and will include the following analyses:

- The time-normalized number of HAE attacks presented descriptively by treatment.
- Pairwise comparisons by using a two-sided Mann-Whitney test for a difference in the time-normalized number of HAE attacks between **CCI** mg CSL312 or **CCI** mg CSL312 q4wk for subjects with C1-INH HAE and placebo q4wk (the test will only be applied to the interim analysis after all subjects completed the blinded part of Treatment Period 1).
- Mann-Whitney test for the difference in the time-normalized number of HAE attacks between the 2 treatments **CCI** mg and **CCI** mg CSL312 q4wk for subjects with C1-INH HAE (the test will only be applied to the interim analysis after all subjects completed the blinded part of Treatment Period 1).
- By-subject listing for primary efficacy.
- **CCI** **CCI**.
- The number and percentage of responders and non-responders with corresponding 95% CI and corresponding by-subject listing.
- **CCI** **CCI**
- The number and percentage, and the fraction of subjects who do not experience a HAE attack at certain time points as well as the median time of being attack-free and corresponding by-subject listing.

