## 8 Data Handling Conventions

### 8.1 Missing Data

#### 8.1.1 Imputation of Non-Date Missing Data

Missing data occurs when any requested data is not provided, leading to blank fields on the collection instrument. These data will be indicated using a “blank” in subject listing displays. Answers such as “Not applicable” and “Not evaluable” are not considered to be missing data and should be displayed as such.

Only missing values for the primary efficacy endpoint (i.e., time-normalized number of HAE attacks) during Treatment Period 1 will have an impact on the analyses of the pairwise comparison between **CCI** mg CSL312 q4wk versus placebo q4wk and **CCI** mg CSL312 q4wk versus placebo q4wk in Treatment Period 1. The time-normalized number of HAE attacks will only be missing for subjects receiving investigational product q4wk and q2wk who drop out before Day 6 and Day 15, respectively, of Treatment Period 1.

Imputation methods based on Markov-Chain Monte Carlo (MCMC) techniques assume a certain distribution of the data and sample from this distribution values which are imputed to replace the missing values. With only 8 subjects per treatment, MCMC methods are not expected to yield reliable estimates. Instead a systematic approach (Enhanced Tipping Point

analysis [[Liublinska and Rubin, 2014](#)]) will be applied to investigate the robustness of the study's conclusion to the assumed missingness pattern. For details see Section [10.1.1](#).

Subjects with the assessment of treatment relationship for AEs and SAEs missing will have the worst case assumed to impute the relationship: if relationship to study treatment is missing and the event started on or after the first administration of study treatment it will be assumed to be "Yes". There will be no other imputation for missing data.

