### 8.2.8 Study Periods Relative to Treatment

The following definitions for the evaluation periods of efficacy and safety will be used to define the durations used in the denominator of the time-normalized endpoints and safety endpoints such as exposure and subject-years. It is not intended to re-assign assessments made during scheduled visits based on these definitions. Scheduled visits will not be re-labelled based on subject's study days irrespective of whether the visit takes place in the planned time window.

The Study Completion Date Visit in this study is at the end of Treatment Period 1 or Treatment Period 2 or at the time of premature study discontinuation. This visit is followed by the Follow-up Visit which may be waived in place of a telephone contact.

**Efficacy Analysis:** The evaluation periods will be:

**Run-in Period (all subjects):** From Week 1 Day 1 of the Run-in Period until the date / time of the Week 1 Day 1 Visit of Treatment Period 1 (the date / time of the first administration of

investigational product in Treatment Period 1) or the Study Completion Visit date and time (whichever occurs earlier). The duration (days) of the Run-in period will be:

Week 1 Day 1 Visit date and time of Treatment Period 1 or Study Completion Visit date and time – Week 1 Day 1 Visit date and time of Run-in + 1.

**Treatment Period 1 (subjects who receive an IV loading dose of investigational product):** From Week 1 Day 6 Visit of Treatment Period 1 (the date / time of the first SC administration of investigational product in Treatment Period 1) until the date / time of the Week 13 Day 91 Visit (the date / time of the first administration of investigational product in Treatment Period 2) or the Study Completion Visit date and time (whichever occurs earlier). The duration (days) of the efficacy evaluation period for Treatment Period 1 will be: Week 13 Day 91 Visit date and time or Study Completion Visit date and time – Week 1 Day 6 Visit date and time + 1.

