To account for multiple testing, the alpha level of 5% will be evenly split between the hypotheses tested. Therefore, the [b] mg CSL312 q4wk or [b] mg CSL312 q4wk CSL312 doses will each be evaluated against placebo q4wk at  $\alpha = 0.025$ :

$H_{01}: a_1 = 0$  versus  $H_{11}: a_1 \neq 0$

and

$H_{02}: a_2 = 0$  versus  $H_{12}: a_2 \neq 0$

In the above hypotheses, the term “ $a_1$ ” is the shift between the 2 distributions of [b] mg CSL312 q4wk and placebo q4wk and the term “ $a_2$ ” is the shift between the distributions of [b] mg CSL312 q4wk and placebo q4wk, respectively.

For the difference in the primary endpoint between the 2 treatments [b] mg and [b] mg CSL312 q4wk in Treatment Period 1, a comparison will be performed as an [b] using a two-sided Mann-Whitney test at  $\alpha = 0.05$ :

$H_{03}: a_3 = 0$  versus  $H_{13}: a_3 \neq 0$

where the term “ $a_3$ ” is the shift in the 2 distributions of the 2 CSL312 doses compared against each other.

There will be no testing of the [b] mg CSL312 q4wk dose against placebo q4wk. The time-normalized number of HAE attacks will be presented descriptively only.

A by-subject listing will be generated as specified in Section 7 and in addition showing the subject reported HAE symptoms, the HAE attack identifier as entered by the investigator with start and end date and time and duration (days), HAE attack location(s), and severity. HAE attacks with a start date falling into the efficacy evaluation period and HAE attacks treated with on-demand treatment for HAE attacks will be flagged. Details of the on-demand treatment will be provided in another by-subject listing. Derived efficacy variables such as number of HAE attacks and the time-normalized number of HAE attacks per month for each treatment period and for both treatment periods for subjects who received the same dose will be presented in another by-subject listing.

### 10.1.1 Sensitivity Analysis for Primary Efficacy: Missing Values for the Time-normalized Number of HAE Attacks in Treatment Period 1

To assess the impact of missing data for the primary efficacy variable a systematic approach will be applied. Imputation techniques based on MCMC methodology are considered inappropriate for this study with very small sample size.

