For each treatment (i.e., placebo q4wk, [REDACTED] mg, or [REDACTED] mg CSL312 q4wk), a range of values for the number of time-normalized HAE attacks per month from 0 to 6 subdivided into 9 increments between two consecutive integer values will be generated. For the two comparisons of active treatment versus placebo all possible combinations from the subdivided ranges will be imputed to replace the missing values and the data will be analyzed using the Mann-Whitney test. Results will be classified into negative (i.e., placebo significantly better), neutral (i.e., no significant difference) and positive (i.e., active treatment significantly better) and depicted in a table and 2 graphs where the x-axis presents the subdivided range for placebo and the y-axis the subdivided range for the active treatment. The different outcomes will be distinguished by different symbols. This will only be applied to the ITT population.

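### Optional, low-cost improvement: the even 0.025 split is valid, but a Holm step-down holds the same 5% familywise error and can only add a significant result for the second dose

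*SAP*

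**What the plan says.** Four places set the rule: the Protocol Synopsis (Primary Endpoint Analysis), Protocol 10.3.2.1.1, SAP 4.2.1 and SAP 10.1. SAP 10.1 has: "To account for multiple testing, the alpha level of 5% will be evenly split between the hypotheses tested". SAP 4.2.1 has: "To account for multiple testing, the alpha level of 5% will be evenly split between the two hypotheses tested". The Synopsis, Protocol 10.3.2.1.1 and SAP 10.1 follow the even-split sentence with a second one that fixes 0.025 for each dose against placebo. No readable text passes alpha to the second test after the first has succeeded.

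The sample size uses the same level (Protocol 10.1): "Alpha is 2.5% for each of the 2 two-sided Mann-Whitney Tests of" the two doses against placebo. SAP 4.5 adds the distribution: "For the time-normalized number of HAE attacks during CSL321 treatment and placebo a Poisson distribution is assumed".

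The tipping-point analysis in SAP 10.1.1 classes results as negative, neutral or positive and shows them in "2 graphs where the x-axis presents the subdivided range for placebo and the y-axis the subdivided range for the active treatment". It gives no alpha.

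On timing, SAP 4.6.1 says of the confirmatory test: "It will only be performed for the interim analysis", meaning the one held when the blinded C1-INH arms have finished Treatment Period 1.

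**The concern.** Under a fixed split, a dose with a p-value between 0.025 and 0.05 is not significant even when the other dose has already been shown to work. Holm would let that dose be tested at 0.05 with no loss of familywise control. With 8 subjects per arm and no replacement of dropouts (Protocol 4.2.3), p-values in that range may be common.

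What is at stake is a confirmatory statement for the second dose. With an assumed between-subject CV of 71%, the split leaves exactly one of two equally effective doses significant in 23.0% of trials at n=7 and 20.4% at n=8. Holm leaves 11.3% and 9.6%. A reader could mistake such a result for a difference between the doses.

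**Working it through.** **Inputs.** Familywise alpha 5%, two two-sided Mann-Whitney tests, one shared placebo arm (SAP 10.1). Rates of 2.9 attacks per month on placebo and 0.6 on either tested dose; 7 evaluable and 8 randomised per arm (SAP 4.5). The efficacy window starts at Day 6 ("From Week 1 Day 6 Visit of Treatment Period 1 (the date / time of the first SC administration of investigational product", SAP 8.2.8) and ends at Day 91, so 91 − 6 = 85 days and 85 / 30.4375 = 2.79 months. The documents give no between-subject variation, so the CVs below are assumptions.

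**The plan's own figures.** Alpha: 0.025 + 0.025 = 0.05, so the split reproduces. The stated power of ~82% with 7 per arm does not. One-month Poisson counts at two-sided 0.025 give about 71% (exact), 72% (normal approximation, continuity-corrected), 76% (uncorrected) and 77% (mid-p). This point does not rest on the ~82%.

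**Why Holm controls the error.** If neither dose works, a false rejection needs the smaller p-value to be at or below 0.025, which has probability at most 0.025 + 0.025 = 0.05. If only one dose works, a false rejection needs the ineffective dose's p-value to be at or below 0.05, which has probability at most 0.05. Neither step uses independence, so the shared placebo arm does not matter. Any p-value at or below 0.025 is rejected under both rules, so Holm never loses a rejection.

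**Size of the gain.** Simulation of 100,000 trials per cell (Monte Carlo SE at most 0.16 points), exact permutation p-values with midranks, both doses at 0.6 per month, gamma-distributed subject rates where CV is above 0. Chance that both doses are significant, split to Holm:

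| Counting window and CV | n=7 | n=8 |
|---|---|---|
| 85 days, Poisson, CV 0 | 99.1% to 99.7% (+0.6) | 99.8% to 99.9% (+0.1) |
| 85 days, CV 50% | 76.6% to 85.3% (+8.7) | 85.4% to 91.5% (+6.1) |
| 85 days, CV 71% | 51.0% to 62.7% (+11.7) | 61.6% to 72.3% (+10.7) |
| 85 days, CV 100% | 24.5% to 34.2% (+9.7) | 31.3% to 41.5% (+10.2) |
| One month, Poisson, CV 0 | 59.8% to 71.8% (+12.0) | 72.3% to 82.0% (+9.7) |

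The gain is not monotone. At n=8 over 85 days it falls to about 5.5 points at CV 150% and about 2.5 at CV 200%, because power itself collapses. The SAP does not say whether the test is exact or approximate. With the normal approximation, CV 71% gives 48.2% to 60.4% (n=7) and 58.2% to 70.5% (n=8).

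**What does not change.** At CV 71% and n=7, at least one dose is significant in 51.0 + 23.0 = 74.0% of trials under the split and 62.7 + 11.3 = 74.0% under Holm. Average per-dose power equals (both + at least one) / 2, so it rises by half the gain in both. In the one-month model at n=7 that is 70.7% to 76.7%, or +6.0, half of +12.0.

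**Error rates over 85 days.** With no effective dose, familywise error is the same under both rules: 3.8% (n=7) and 4.0% (n=8) at CV 0, 4.1% and 4.3% at CV 71%. With one effective dose, false rejection of the other rises from 2.0% to 4.3% (n=7) and from 2.2% to 4.5% (n=8) at CV 0, and stays inside 5%. Dropout and Run-in selection are not modelled.

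**The case against.** The split is valid, prespecified and consistent with the sample-size alpha. The primary objective is efficacy of the product, not success of both doses. Under the SAP's Poisson assumption over the real window there is almost nothing to gain, and the larger 85-day gains rest on CVs that the documents do not give. All of this stands, and it is why the change is optional.

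The split also has practical merits. Each dose is decided on its own, which suits the two separate tipping-point graphs, and simultaneous intervals are simple. The readable text plans intervals per arm only (SAP 10.1). SAP 10.1.3 to 10.1.5 are redacted, so any such use there cannot be checked.

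Timing is the strongest objection. Unblinded IDMC outputs go to some sponsor personnel and include attack timelines from the second review, planned for end of February 2019 (SAP 4.1, 4.6.2). SAP 2.0 is dated 19 June 2020. Treatment Period 2 is open-label, and two q4wk arms continue their dose (SAP 4.4), so attack data by dose accrue early. A reader might infer that any change is already too late. Protocol 3.4 implies about 119 − 83 = 36 weeks of entry, so the last subject would finish Treatment Period 1 about 36 + 4 + 8 + 13 = 61 weeks after first screening. If screening began by December 2018 (an assumption), that is about February 2020. But actual enrolment is not reported, and SAP 4.6.1 still writes of the test as future. The documents leave this open.

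**Conclusion.** The point holds as an optional, low-cost improvement. Holm's validity and its dominance over the split in rejections rest on no assumed figure. The size of the gain depends on both the counting window and between-subject variation: under 1 point at the SAP's rates over 85 days with pure Poisson counts, about 10 to 12 points with one-month Poisson counts, and about 6 to 12 points over 85 days at assumed CVs of 50% to 100%.

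Three stronger readings are tempting and unsupported. First, that the split is wrong or that the shared placebo arm undermines it: it controls the familywise error at 5%. Second, that it risks choosing the wrong dose: Protocol 3.3.1 says the data will inform dose choice but does not tie that choice to significance. Third, that the change is free: it needs an amendment and evidence that it was made blind.

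**What to change.** In the Protocol Synopsis, Protocol 10.3.2.1.1 and SAP 10.1, replace both the even-split sentence and the sentence after it that fixes 0.025 for each dose. Changing only the first would leave two contradictory rules. In SAP 4.2.1 replace the even-split sentence. Use in each place: *The smaller of the two p-values is tested at 0.025; if it is significant, the other is tested at 0.05; otherwise testing stops.*

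Keep 2.5% per test in Protocol 10.1 and SAP 4.5 as the planning basis.

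In SAP 10.1.1 state an alpha of 0.025 per comparison and keep the three classes and both graphs. If points with p between 0.025 and 0.05 are shown separately, give them different symbols by direction and note that they count only if the other dose is significant at 0.025.

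Cost: seven sentences in four places (3 × 2 + 1), hence a protocol amendment and a SAP update (SAP 5 provides for both), plus the tipping-point convention. No subjects or data are added. In exchange, simultaneous intervals become less simple and one dose's decision can depend on the other's.

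Adopt it only if it is documented before the confirmatory test at the first interim analysis, by staff with no access to unblinded IDMC outputs or to Treatment Period 2 attack data by dose. If that cannot be shown, keep the even split and make only the SAP 10.1.1 alpha clarification.

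### The tipping-point grid in SAP 10.1.1 is capped at 6 attacks per month; if an observed placebo rate reaches or exceeds 6, the worst rank for a missing active-arm subject is not tested

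*SAP*

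**What the plan says.** SAP 10.1.1 takes placebo and the two tested CSL312 q4wk doses. For each it generates candidate rates "from 0 to 6 subdivided into 9 increments between two consecutive integer values", imputes all combinations for the missing subjects, repeats the Mann-Whitney test and classes each result as negative, neutral or positive. SAP 8.1.1 gives the purpose: "to investigate the robustness of the study's conclusion to the assumed missingness pattern". It adds that a q4wk subject's rate is missing only if the subject drops out before Day 6 of Treatment Period 1.

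The plan gives no reason for the limit of 6, no rule for observed rates above it and, in the readable text, no worst-rank imputation.

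The sizing inputs are in SAP 4.5. The placebo assumption reads "The time-normalized number of HAE attacks is 2.9 attacks per month during treatment with placebo", obtained "using the lower bound of the distribution-free 95% confidence interval (CI) for the median of the first placebo treatment period". The active rate is 0.6 per month, and "a Poisson distribution is assumed" for both. Protocol 4.1.1 and 4.1.3 require minimum attack frequencies before Screening and during Run-in (at least 4 in 2 months; at least 2 in 4 weeks) but set no maximum.

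**The concern.** A tipping-point analysis is informative only if it reaches the least favourable plausible value. In a rank test, that value for a missing active-arm subject is any rate above every observed placebo rate. With a fixed limit of 6, a placebo subject above 6 always outranks the imputed subject, and one at exactly 6 ties with it at best. The table and graphs could then show positive at every point although a tipping point lies just outside the grid. A reader would take that as robustness to missing data when it reflects where the grid stops.

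The limit sits about twice above a placebo rate that is itself a lower confidence bound for a median, in a population selected for frequent attacks.

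**Working it through.** **1. Reproduce the plan's figure.** The plan states no figure for the tipping-point analysis, so the check is on its sizing model: Poisson 2.9 versus 0.6, 7 per arm, "Alpha is 2.5% for each of the 2 two-sided Mann-Whitney tests". P(placebo > active) + ½P(tie) = 0.894, so the log odds are ln(0.894/0.106) = 2.135. In the O'Brien-Castelloe approximation, power = Φ[(√N × log odds − z × s₀)/s₁], with N = 14, z = 2.241, s₀ = 2.252 and s₁ = 3.218. This gives Φ[(7.990 − 5.048)/3.218] = Φ(0.914) = 0.820, which matches the stated ~82%. Direct simulation of the test at n = 7 gives about 71% to 76%; that is a separate matter.

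**2. How likely is a placebo rate above 6?**
- Plan's monthly Poisson(2.9): P(>6) = 0.0287 per subject; for any of 8, 1 − (1 − 0.0287)⁸ = 20.8%. A rate of exactly 6 would tie with the top grid value and is not counted here.
- Poisson over 85 days (Day 6 to Day 91): the expected count is 2.9 × 85/30.4375 = 8.10. A rate above 6 needs more than 6 × 85/30.4375 = 16.8, so 17 attacks or more. P = 0.0042 per subject, 3.3% for any of 8.
- Gamma variation between subjects (assumed shape 4, 2, 1) at mean 2.9: 41%, 58%, 70%.
- Assumed mean 4.0: 40% (Poisson), 86% (shape 2), 87% (coefficient of variation 0.8).
- Short follow-up: SAP 8.2.8 ends the period at study completion if earlier and states no minimum length. One attack in under 30.4375/6 = 5.1 days, or two in under 10.1 days, gives a rate above 6.

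**3. Can a tip be hidden?** Exact 8 versus 8 test at 0.025: U = 10 is significant (p = 0.0207), U = 11 is not (p = 0.0281). A constructed example with one active value missing:
- Placebo: 7.2, 4.3, 3.9, 3.2, 2.9, 2.5, 1.8, 1.1.
- Active, observed: 0, 0.35, 0.4, 0.7, 0.75, 1.4, 2.1.

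Count the pairs in which active exceeds placebo. The observed values give 3 (1.4 beats one placebo value, 2.1 beats two). Imputing 6.0 adds 7, so U = 10 and the result is significant. Imputing 7.5 adds 8, so U = 11 and it is not. With a step of 0.1 (nine points between integers), all 61 grid values are positive, yet the worst rank is neutral. The continuity-corrected asymptotic test gives the same verdicts (0.0239 and 0.0313).

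**4. How often?** Simulation given exactly one missing active value, 7 observed active and 8 placebo, continuity-corrected test at 0.025. A hidden tip means significant at 6.0 but not at the worst rank. The gamma shape is the same in both arms.

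| Model (placebo/active mean per month) | Any placebo >6 | Hidden tip, % of trials | % of results positive at 6.0 |
|---|---|---|---|
| Plan's monthly Poisson 2.9/0.6 | 21% | 4.1% | 12.8% |
| Poisson over 85 days 2.9/0.6 | 3% | 0.2% | 0.2% |
| Gamma shape 4, 2.9/0.6 | 41% | 5.1% | 11% |
| Gamma shape 2, 2.9/0.6 | 58% | 6.5% | 26% |
| Gamma shape 1, 2.9/0.6 | 70% | 5.1% | 44% |
| Gamma shape 2, 4.0/0.6 | 86% | 15.5% | 30% |
| Gamma shape 2, 4.0/1.2 | 86% | 10.5% | 50% |

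A run with placebo mean 4.0 and coefficient of variation 0.8, active mean 0.6 and coefficient of variation 1.0, and the asymptotic test gave the highest figure, 16.2%.

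**5. More than one missing value.** With two active values missing, or one in each arm (placebo set to 0), the existing grid already leaves positive in about 92% to 100% of trials. The cap then hides a tip in only 0% to 8%.

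**The case against.** The strongest reply is that the trigger is rare. A q4wk rate is missing only for a dropout between the IV loading dose and the first SC dose; later dropouts keep a rate. As an illustration, suppose the one dropout per arm allowed for in SAP 4.5 falls evenly over 13 weeks. The chance that it falls in the first 5 days is 5/91 = 5.5%. Multiplied by 0.2% to 16%, that is about 0.01% to 0.9% per comparison. This stands and limits the point.

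The reply also has force against three stronger readings:
- A reader might infer that the worst rank is never imputed. That is not so: if every placebo rate is below 6, imputing 6.0 already ranks the missing subject above all placebo subjects. For a missing placebo subject the unfavourable value, 0, is inside the grid.
- A reader might infer that this is the only planned check of the primary result against missing data. That cannot be shown: SAP 10.1.3 to 10.1.5 are redacted, and 10.1.2 plans a review of subject profiles for missing-value patterns due to dropouts.
- A reader might take the higher simulated rates as the size of the problem. They rest on between-subject variation and a 4.0 mean that the documents do not give; the document-based cases are 0.2% and about 4%.

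The by-subject listings would also show any placebo rate above 6, so an alert reader could notice the cap. That does not correct a table that is positive at every point.

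**Conclusion.** The point holds in a narrow form. The grid has a fixed upper limit with no stated basis and no extension rule, and the example shows that it can report robustness where a tipping point exists. Three things must coincide: an active q4wk dropout before Day 6, an observed placebo rate at or above 6, and a borderline test statistic.

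Given one such dropout, the hidden-tip rate runs from 0.2% (Poisson over 85 days) through about 4% (the plan's sizing model) to about 16% (assumed variation with a 4.0 mean). The true position in that range depends on the between-subject spread of placebo rates, which the documents do not report. The primary test itself is unaffected. This is a minor improvement, worth making because it costs so little.

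**What to change.** In SAP 10.1.1, either:
- let the grid run from 0 to the larger of 6 and one step above the highest observed rate in the two compared arms; or
- keep 0 to 6 and add one worst-rank point, with each missing active subject ranked above all observed values.

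Either is a one-phrase change and a few more runs of the same test. The first can lengthen the table and stretch the plot axes if a short follow-up yields an extreme rate; the single worst-rank point avoids that and is the simpler choice.
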